4.2 Sample Size

We will recruit a voluntary sample of 80 HHSPs that will be randomized to either the experimental or AC arm. We have selected this sample size given previous work which indicates that 40 HSSPs per arm would provide 80% power to detect a moderate (0.5 SD – to – 0.6 SD) effect size, which is indicative of a clinically significant outcome (40).

As of March 2023, we are now focusing on achieving sample size aims for one of the two arms of the study and no longer going to evaluate the facilitator-led VEGA. Our primary aim will be achieved by conducting a one-arm pilot trial of 40 veteran-serving HHSPs where participants will complete self-directed VEGA. In following this algorithm, our team will be able to consider the needed recruitment and retention rates to successfully implement a definitive education trial.

4.3 Qualitative Analyses

Transcripts of qualitative interviews, as well as associated field notes, will be managed in Nvivo and analyzed using reflective thematic analysis and constant comparison (41, 42). Reflective thematic analysis via constant comparison and analytic memo-ing will allow for the identification codes, categories, and themes related to implementing and evaluating the VEGA resources among HSSPs working with or who have worked with veterans and their family members (41, 42).

4.4 Integration of Qualitative and Quantitative Data for Interpretation

After conducting separate quantitative and qualitative analyses, quantitative and qualitative data will be integrated for interpretation. Quantitative acceptability and feasibility metrics will be mapped to excerpts of qualitative data on perceived acceptability or educational burden via a mixed method joint display; this display will support a comprehensive interpretation of the extent to which a definitive trial examining VEGA in our sample population is tenable. A separate joint display will cross-tabulate scores on secondary outcome measures with qualitative excerpts of VEGAs perceived value and impact for improving provider knowledge and skills related to IPV and CM alongside a narrative description of findings that integrates our conceptual frameworks for continuing education among HSSPs working with or who have worked with the veteran population (41-43).

5.0 Safety Parameters and Reporting

5.1 Time requested of Participants

Participants will be asked to complete a 15-minute screening call with a RA to determine their eligibility for the study and collect sociodemographic information. Participants randomized into one of the two VEGA education intervention arms will either attend one three-hour session (if in AC arm) or complete approximately three hours of module content online on their own time, within a one-week period. All participants will also be asked to complete three surveys as part of the quantitative research assessments, at baseline (Time 1), post-education (Time 2), and 3 months follow-up (Time 3). The Time 1 survey will take ~30 minutes to complete, the Time 2 survey ~20 minutes to complete and the Time 3 survey ~30 minutes to complete. The time needed to complete one survey will be tracked for the study to better estimate this burden for a future RCT.

Participants who complete all three survey timepoints (baseline, post-intervention, and 3-month follow-up) will receive a \$120.00 gift card to Amazon, Mastercard or Indigo as a token of appreciation for the completion of three quantitative research assessments.

A sub-sample of the participants (n=30) will participate in the qualitative interview which we expect to take approximately 60 minutes. Each qualitative participant will receive a \$60.00 gift card to Indigo, Mastercard or Amazon as a token of appreciation for the completion of the interview.

Table 2: Timepoint Compensation Schedule

Timepoint (data type)	Approximate Length	Compensation for participation (in gift cards):
Screening (survey)	15 minutes	\$0
Baseline (Time 1; survey)	30 minutes	\$40
Post-education (Time 2; survey)	30 minutes	\$40
3-month follow-up (Time 3; survey)	30 minutes	\$40
TOTAL SURVEY COMPENSATION (All participants)	105 minutes	\$120
Interview (Time 2 or Time 3)	60 minutes	\$60
TOTAL COMPENSATION (n=30)	165 minutes	\$180

Centre of Excellence VEGA Training and Research Project

Completion of the Child Maltreatment Knowledge and Skills Questions developed by the VEGA team and Satisfaction with VEGA training (which will be referred to as “accreditation questions”) and the self-directed VEGA training has been accredited for 3 MOC credits through the RCPSC and 3 Mainpro+ credits through the CFPC. Certificates of completion can be used for continuing medical education credits through the RCPSC (all physicians except family physicians) or the CFPC (family physicians only) or submitted to practitioner’s college or association for continuing education credit (social workers and any other health professional). All accreditation requirements and administration of certificates will be managed by the VEGA Project.

In addition, providers will receive unrestricted access to *self-directed VEGA* upon completion of the study (i.e., after all qualitative and quantitative data have been collected) to ensure all enrollees have ongoing, indefinite access to the educational information offered by the VEGA educational resources.

5.2 Potential Risks and Plans to Mitigate Risks

5.2.1 Adverse events

The focus of this research is an educational intervention for regulated health and social service providers. Given this information, conducted participation in either arm of the pilot RCT involves minimal risk.

Adverse events are any untoward health-related outcomes that occur during the study, regardless of how related they are to the study intervention. Facilitators and research staff directly interacting with participants will use their training to identify and mitigate all potential participant risks, including ones that may not be directly associated with study participation.

Anticipated adverse events which are relevant to this study include those related to healthcare and social service providers (HSSPs) safety and wellbeing include:

- HSSPs own experience(s) with intimate-partner violence and/or child maltreatment, which may raise or contribute to distress during the educational intervention or during research activities.
- HSSPs experience(s) providing care to veterans or their family members who have experienced intimate-partner violence and/or child maltreatment, which may be distressing.

Anticipated adverse events that are not serious will be discussed as needed by research staff with the Principal Investigators, if the nature of the adverse event is considered to signal unresolved risk to the participant. Emergency medical services will be alerted as required if there is concern about imminent risk to life of an adult or safety of a child. The Principal Investigator, who is a registered and regulated social worker and psychotherapist, will follow regulated reporting requirements as necessary, as well as determine if other steps are needed to mitigate risk to the participant.

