2.2.4 Education Intervention

Self-Directed VEGA – Experimental Arm uses an approach where participants complete the Violence, Evidence, Guidance, Action Project (VEGA) content online as a self-directed educational activity, at their own pace in a series of modules. Individuals will register to access the VEGA Education Resources site at <https://vegaproject.mcmaster.ca/>. Registration will be free. They will be asked to provide their name and email to be sent the online resources. They will also be asked to agree to terms of use to access this site. Participants will be sent an information sheet that outlines the steps to register and access the VEGA materials online [“CoE_VEGA_SelfDirectedRegistration_V6_03MAR2023.”]. Participants have the option of completing the self-directed VEGA arm in either English or French as the VEGA Educational Resources site offers the content in French and English. The consent form will inform participants this is an option for the self-directed VEGA arm only. The information sheet for registering for self-directed VEGA will also show participants how to access the French version of the VEGA online modules [CoE_VEGA_SelfDirectedRegistration_V6_03MAR2023.”].

Participants will be asked to direct all content-related questions to the RC who will forward them to the VEGA team to see if they can be answered. Participants will be provided the contact information for the VEGA IT Team who will address any technology-related questions they may have while completing the self-directed VEGA program [see “RISE with Veteran Service Providers – Training Program Assignment” in CoE_VEGA_EmailScripts_V8_12MAY2023]. If they haven’t completed them already, participants will receive reminders via email every two days from the RC reminding them to complete the self-directed VEGA online modules [see “RISE with Veteran Service Providers – Online Modules Reminder” in CoE_VEGA_EmailScripts_V8_12MAY2023”].

Participants will be asked to complete the self-directed VEGA at their convenience, within one week of when they are informed they have been asked to complete the self-directed VEGA program. It will take approximately 3 hours for participants to complete all modules.

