Facilitator-Led VEGA – Active Control Arm uses a group-based approach where participants complete the Violence, Evidence, Guidance, Action Project (VEGA) content as a virtual or face-to-face workshop (i.e., *facilitator-led VEGA*). In this study, all workshops will be virtual to prevent social gathering during COVID-19. The AC intervention will be facilitated via Zoom technology, by two trained facilitators with between 15 to 20 participants in each workshop (keeping the recommended 10:1 participant-to-facilitator ratio) and will last approximately 3 hours. The workshop approach is delivered by trained facilitators and is standardized via the use of a flexibly structured facilitator's guide.

As of March 2023, no participants will be asked to complete facilitator-led VEGA, as we are removing this arm from the study.

VEGA training takes approximately 3 hours to complete and pedagogical elements for both approaches have been informed by education scholarship. Below is a table outlining the common pedagogical elements in the self-directed and facilitator-led VEGA education interventions (Table 1).

Table 1: Pedagogical Elements of Self-Directed VEGA (i.e., experimental arm) and Facilitated VEGA (active control arm) Educational Approaches

Pedagogical Elements	Self-Directed VEGA (Experimental Arm)	Facilitator-Led VEGA (Active Control Arm)
Didactic Material[45]	Asynchronous reading	Synchronous lecturing
Deliberate practice[46, 47]	Case-Based Animated Simulations	Case-Based Role play
Enabling learning tools [48]	Virtual Patients, Clinical Handbook, Clinical Scripts	Virtual Patients, Clinical Handbook, Clinical Scripts
Test-enhanced learning [43]	Individual multiple-choice questions with response feedback	Group-based polling (i.e., multiple-choice) and feedback.

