3.1.2 Quantitative Assessments

A trained research assistant (RA) will gather all data from all participants during three study assessment time points. Quantitative assessments will be hosted on REDCap and will be available online using a web-based link and emailed to participants at three time points: the week before they begin the VEGA training (Time 1), post-education (Time 2), and 3-months after the Time 1 survey is completed (Time 3). Participants will be asked to complete the surveys within one week, from the date they are initially sent, on their own time. Time 1 surveys will be sent

Centre of Excellence VEGA Training and Research Project

after completing the consent form, Time 2 will be sent the day after the online modules are due to be completed (experimental arm), and Time 3 will be sent 3 months after this date, to be completed within two weeks. Each survey will take approximately 30 minutes to complete. A detailed list and description of study measures can be found below. The format of all of surveys, listing all of the questions in each questionnaire can be found in [“CoE_VEGA_QuantitativeSurvey_V3_12MAY2022”]. Due to changes in requirements for continuing education credits, we created an alternative version of the survey [“CoE_VEGA_QuantitativeSurveyB_V3_24MAR2023”] that excludes the measures “Child Maltreatment Knowledge and Skills Questions developed by the VEGA team” and “Satisfaction with VEGA training” because the VEGA team will administer questions required for continuing education credits. As of March 2023, all participants in the study will be administered this version [CoE_VEGA_QuantitativeSurveyB_V3_24MAR2023], we will not be administering the original version [CoE_VEGA_QuantitativeSurvey_V3_12MAY2022]. As a courtesy, participants will also have the option of completing the surveys in either English or French. Before each survey, they will be asked if they would like to complete the current survey in English or French.

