5.2.2. Serious Adverse Events

Centre of Excellence VEGA Training and Research Project

Serious Adverse Events (SAEs) are defined within this study as any untoward health-related outcome in the study occurring towards a participant that:

- Results in death;
- Is life-threatening (an event in which the participant was at risk of death at the time of the event; it does refer to an event which hypothetically might have caused death if it were more severe);
- Requires inpatient hospitalization or prolongation of an existing hospitalization.
- Results in persistent or significant disability/incapacity

SAEs may be reported by participants or other authorities (e.g., child protection) to research staff or investigators. Serious, yet anticipated study relevant events include hospitalization of a participant due to mental illness; participant suicide; participant hospitalization; life-threatening injury of a participant; participant death. Research staff members will also receive SAE report forms to complete following communication with research participants or collaborators. SAEs will be tracked in an excel database and communicated, as appropriate to the HiREB. In the case of anticipated serious events, providers within our partner organizations or research staff will notify the Principal Investigators as soon as possible, within two business days, or earlier if the provider or research staff member determines that investigator guidance is required to safeguard the safety of the participant or research staff member.

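### Detection of non-serious adverse events, including the distress the protocol itself anticipates, relies on unsolicited observation; the one-arm redesign extends this to every participant and the safety section was not revised

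*Combined protocol and SAP*

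**What the plan says.** Section 5.2.1 defines adverse events broadly, whether or not they are related to the intervention. The anticipated ones both concern distress in the provider: from the provider's own history of violence, "which may raise or contribute to distress during the educational intervention or during research activities", or from caring for affected veterans and families. Detection is assigned as follows: "Facilitators and research staff directly interacting with participants will use their training to identify and mitigate all potential participant risks". For handling, "Anticipated adverse events that are not serious will be discussed as needed by research staff with the Principal Investigators", and then only where the event points to a risk that has not been resolved.

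Serious events are treated differently in section 5.2.2. Staff receive report forms, and "SAEs will be tracked in an excel database and communicated, as appropriate to the HiREB". Participants, outside authorities and providers in partner organizations may also report them.

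Section 2.2.4 states that, as of March 2023, "no participants will be asked to complete facilitator-led VEGA, as we are removing this arm from the study". The arm that remains delivers its "content online as a self-directed educational activity, at their own pace in a series of modules". Section 3.1.2 sends all three surveys as emailed REDCap links. Section 5.3 has staff pass on concerns that arise in their dealings with participants, requires mitigation actions and their outcomes to be documented, and places helplines at both ends of the survey.

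**The concern.** Section 5.2.1 was written for a two-arm trial in which one arm met facilitators live. It still names facilitators and still speaks of participation in one or other arm of a randomized trial. In the current design nobody is with the participant during training, and no step is described that asks the participant how it went in terms of harm.

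Two things are at stake. First, a distressed participant who does not volunteer it may not come to the Principal Investigator's notice, because the section 5.3 pathway starts from something that staff have noticed. Second, the pilot is meant to inform a definitive trial. If few or no events come to light, the team could not tell a well-tolerated intervention from one whose effects were not looked for. Section 3.1.1 counts dropouts but does not mention recording reasons, so withdrawal because of distress would appear only as attrition.

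**Working it through.** The plan states no adverse event rate, count or detection probability, so there is no figure to reproduce. The check compares the contacts that the plan schedules with what each could detect, and then works out what a zero count would mean.

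**Contacts in the one-arm design**

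| Contact | Section | Could it reveal training-related distress? |
|---|---|---|
| Screening by call or online form | 2.2.2 | No, before training |
| Consent review with the research assistant | 2.2.2 | No, before training |
| Email reminders every two days; content questions to the coordinator | 2.2.4 | Only if the participant volunteers it |
| Time 1 survey | 3.1.2 | No, before training |
| Time 2 and Time 3 surveys | 3.1.2, 3.2 | No described measure asks about it |
| Interview, 15 after training and 15 at 3 months | 3.1.3 | Possibly; purpose is qualitative, run by a contract interviewer |

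The satisfaction questionnaire, which had short-answer items, left the study survey in March 2023 "because the VEGA team will administer questions required for continuing education credits". Its described content is learning outcomes, materials and usefulness, so its removal is only a small part of the case.

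**Live-contact coverage.** Inputs: N = 40 (section 4.2); 30 interviews split 15 and 15 (section 3.1.3), each person interviewed at Time 2 or Time 3 (Table 2).

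- Interviewed soon after training: 15/40 = 37.5%, leaving 25/40 = 62.5% with no scheduled live contact then.
- Interviewed at either time: at most 30/40 = 75%, leaving at least 10/40 = 25% with none after training.

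**Meaning of a zero count.** The exact one-sided 95% upper limit with no events among n observed people is 1 − 0.05^(1/n).

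- n = 40 (everyone asked): 1 − 0.05^(1/40) = 7.2%
- n = 30 (all interviewees disclose): 1 − 0.05^(1/30) = 9.5%
- n = 15 (only post-training interviewees disclose): 1 − 0.05^(1/15) = 18.1%

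**Chance of seeing no case.** Let p be the true distress rate and s the share of cases that come to light. Then P(none seen) = (1 − p·s)^40. The values of p are assumptions; the documents give none.

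| Assumed p | s = 1 (all cases seen) | s = 0.75 (30 of 40) | s = 0.375 (15 of 40) | s = 0.10 |
|---|---|---|---|---|
| 5% | 0.13 | 0.22 | 0.47 | 0.82 |
| 10% | 0.015 | 0.044 | 0.22 | 0.67 |
| 20% | <0.001 | 0.002 | 0.044 | 0.45 |

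At an assumed 10% rate, four cases are expected among 40. The chance of seeing none is 1.5% if every case is seen and about 22% if only 37.5% of cases are.

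**The case against.** The strongest reply is that passive detection is proportionate for about three hours of training given to regulated professionals in a 40-person feasibility pilot, and that the primary feasibility outcomes do not depend on it. That stands as an argument about severity. It does not explain why the section relies on facilitators who are no longer there, or why the trial's own anticipated risk is never asked about.

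A reader might infer four stronger things that the documents do not support.

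- *That the redesign moved the study online.* It did not. Self-directed VEGA was the online experimental arm from the start, section 2.2.3 already describes the baseline survey as web-based, and the removed arm was itself virtual: "The AC intervention will be facilitated via Zoom technology, by two trained facilitators". What was lost was a live session.
- *That all adverse events depend on facilitators and staff.* Serious events have the further routes in section 5.2.2, though these too are unsolicited.
- *That distress would go unseen.* Participants may raise questions at any time, the coordinator emails them during training, and up to 30 are interviewed on topics that include educational burden, where distress could surface. Detection is weakened, not eliminated.
- *That distress will be reported as absent.* Section 4 plans no adverse event count or safety conclusion, and the minimal-risk statement in 5.2.1 is a judgement made in advance from the nature of the study.

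It is also fair to credit the helplines and the documentation of mitigation actions in section 5.3. Helplines protect participants but tell the study team nothing, and mitigation is documented only after someone has noticed a problem. Finally, the 18.1% bound treats 3-month interviewees as unable to report distress from training. If they can, 9.5% is the relevant figure.

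**Conclusion.** The point holds for non-serious events. Their detection, including that of the named risk of distress, rests on what staff happen to notice or participants happen to volunteer. The March 2023 change removed the facilitators and made this the position for all participants, and section 5.2.1 was not brought into line. A low or zero count could not be read as absence of distress: zero events would be compatible with a rate of up to 7.2% if all 40 were asked, and up to 9.5% to 18.1% if only the 30 or 15 interviewees were effectively observed.

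These bounds assume 40 enrolled, all 30 interviews held, and full disclosure by those counted as observed. With less disclosure they widen. The conclusion also rests on the measures as section 3.2 describes them. The survey and interview guide are cited as separate files and could contain a distress question. If they do, the protocol should say so and connect it to section 5.3. This is an improvement worth making at low cost and does not threaten the primary feasibility outcomes.

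**What to change.** 1. Rewrite the detection sentence in section 5.2.1 for the one-arm design, removing the references to facilitators and to two arms.
2. Add one or two items to the Time 2 and Time 3 REDCap surveys asking whether the training or study activities caused distress and whether any health event has occurred since the last survey, with a free-text box and an option to request contact.
3. State who monitors the answers. Survey data are held under participant ID, but section 6.2.1 gives the coordinator and the research assistant access to the linking document, so either can pass a positive answer to the Principal Investigator through the existing section 5.3 pathway.
4. Log non-serious as well as serious events, and add to section 4 a summary giving the number and percentage among those asked.

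The cost is an ethics board amendment to the survey and probably to the consent form, timely monitoring of responses, some non-serious reports to triage, and probably a less favourable adverse event count. No new staff or systems are needed.
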